3.3 Secondary Study Endpoints

These will include mast cell mediator levels; serum tryptase, urinary leukotriene (LT) E4, n-methyl histamine (N-MH), and 2,3 dinor 11β prostaglandin(PG) F2α levels [Mayo Medical Labs].

3.4 Primary Safety Endpoints

Minimal systemic absorption is expected with each of the active components. Safety endpoints to be measured at the initial and final visits and include Investigator and Participant observation of local skin tolerability including ratings of itching, swelling

stinging/ burning, and dryness on separate scales as none (0), mild (1), moderate (2), or severe (3).

4 Subject Selection Enrollment and Withdrawal

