5.2 Study Procedures

Preparation and Administration of Study Drug

Each participant will receive both verbal and written instructions as to proper dosing and application and storage. The Mayo Clinic Research Pharmacy in Rochester, MN will prepare, store and distribute the study formulation. Participants will receive 2-one-half pound ointment jars of the study formulation. The jars will be returned the final visit.. The returned used jars will be weighed by the Principal Investigator or a study team member to determine the amount used/compliance. Should additional cream be required during the 2 weeks of the study, the patient can contact the principal investigator or the clinical study coordinator. Upon notification from the patient, an extra ½ pound jar will be sent to the patient by overnight express mail.

Instructions will be provided as follows: Twice daily, apply a thin film of the study formulation to symptomatic areas of the skin including about one centimeter of normal appearing skin surrounding each area of involvement. Rub lightly and uniformly into the skin. An investigator will demonstrate correct application by using a bland emollient moisturizer.

Subject Compliance Monitoring

Adherence to the treatment regimen is of great importance. Poor compliance may result from lack of patient understanding, discomfort caused by the product and unrealistic expectations. Assessment of participant compliance will be determined by weighing ointment jars at the time of the final visit. Participants are not expected to use a specific amount of the study formulation . Rather, use will be individualized depending on the amount of symptomatically involved skin. Those who are non-compliant with the study protocol despite additional counseling and the opportunity to correct will be withdrawn.

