6.5 Visit 2-Final visit (Week 2 +/- 1 day)

- a) Reassess cutaneous mastocytosis severity by (Global & Local) SCORMA Indexes; monitor vital signs
- b) Investigator Assessment of Global Improvement
- c) Quality of life assessment:SkinDex-16
- d) Review changes to medical history and current medications
- e) Review contraception (female patients of childbearing potential)
- f) Review adverse events
- g) Review compliance

- h) Repeat photographs
- i) Obtain levels of serum tryptase, urinary N-MH, LTE4, and 2,3 dinor 11β PGF2α
- j) Reconcile study formulation

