7.2.1 Definition of response

Complete response:

Clinically significant SCORMA improvement in all 3 parameters of treated, involved skin: % skin involvement; activity or symptoms &/or

Improvement in all 3 SkinDex-16 domains (Emotions, symptoms, functioning) &/or Resolution of 75% of cutaneous lesions

Near Complete response:

Clinically significant SCORMA improvement in two of 3 parameters of treated, involved skin: % skin involvement; activity or symptoms and/or

Improvement in 2 SkinDex-16 domains (Emotions, symptoms, functioning) &/or Resolution of >50% of cutaneous lesions

Partial Response:

Clinically significant SCORMA improvement in one 3 parameters of treated, involved skin: % skin involvement; activity or symptoms and/or

Improvement in 1 SkinDex-16 domain (Emotions, symptoms, or functioning) &/or Resolution of >25% of cutaneous lesions

No response:

No significant SCORMA improvement in any of 3 parameters of treated, involved skin: % skin involvement; activity or symptoms and/or

Improvement in no SkinDex-16 domain (Emotions, symptoms, functioning) &/or Resolution of no cutaneous lesions.

*Additionally, for primary safety endpoints which will be scored as none, mild, moderate, or severe, the proportion of patients in each category at each follow-up time point will be estimated for each of the different safety endpoints. P-values of 0.05 or lower will be considered as statistically significant.

Handling of missing data

This is a prospective study and therefore we do not anticipate any missing data. In the event of any unexpected missing data, no attempt to impute this missing data will be made; missing data will simply be treated as missing in the statistical analysis.

Multiplicity

Since this is an exploratory pilot study, no adjustment for multiple testing is needed. P-value of 0.05 or lower will be considered as statistically significant.

Primary Hypothesis:

The study seeks to demonstrate the effectiveness and tolerability of a novel topical composition consisting of 3 components (diphenhydramine, aspirin and cromolyn sodium) in a neutral skin moisturizing cream (Vanicream) for the treatment of cutaneous lesions of mastocytosis. This will be determined by the proportion of participants who achieve complete or near-complete response utilizing the SCORMA Index, and SkinDex-16 QOL.

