- •No current use of Interferon Alpha; Cladribine; Imatinib Mesylate; Midostaurin; Avapritinib, Prednisone or other chemotherapy agents.
- •No current use of chemotherapeutic agents
- •Good general health as confirmed by medical history
- •Female patients of childbearing potential with a negative urine pregnancy test who agree to use effective methods of birth control or remain abstinent during treatment
- Patients who are willing and capable of cooperating to the extent and degree required by the protocol
- Patients who read and sign an approved informed consent for this study

The study includes 2 visits over 2weeks. There will be no cost to participate. You will not be compensated for your time.

Who can I contact for more information?

Principal Investigator:	[contact]
[name].	
	Email:
	[contact]
	Address:
	[name]
	[name]
	[name]

Primary Safety Endpoints Table

Patient Name:

[figure not shown]
Symptom (Patient/Physician)	Week→	
	0	2
itching		
swelling		
stinging/burning		
dryness		

none (0), mild (1), moderate (2), or severe (3)

SCORMA INDEX Name of patient Institution Date of birth Physician Date of visit Patient number (8.5)Between brackets: Age under 2 yrs. A: Extent please indicate the area involved [] B: Intensity average representative area Criteria Intensity Intensity items Pigmentation / erythema 0 = absent Vesiculation 1 = mild Elevation 2 = moderate Positive Darier's sign 3 = severe C: Subjective Symptoms Visual Analog Scale (by parents if child < 5 years) 1. Provoking Factor(s) 0 ------ 10 2. Flushing 0 ------ 10 3. Diarrhea 0 ------ 10 Pruritus Localized Bone Pain

[]

Scorma index: A/5 + 5B + 2C/5

LOCAL SCORMA INDEX-FOR AREA(S) TREATED-Indicate Area(s) Treated

of skin treated-INDICATE A	AREA(S) TREATED
Intensity	Intensity Items
[]	0= Absent
	1= Mild
	2= Moderate
	3= Severe
is	
Visual Analog Scale	
0	10
0	- 0
0	10
0	10
0	10
5 + 5B + 2C/5	
	Intensity [] [] [] [] ss Visual Analog Scale 0 0 0 0 0 0

Page 28 of 32 [name]

Clinical Response Assessment: Global SCORMA Assessment

Week	SCORMA	% Resolution	ASSESSMENT			
0						
2						

Complete response:

Clinically significant SCORMA improvement in all 3 parameters of % skin involvement; activity or symptoms &/or

Resolution of 75% of cutaneous lesions

Near Complete response:

Clinically significant SCORMA improvement in two of 3 parameters of % skin involvement; activity or symptoms and/or

Resolution of >50% of cutaneous lesions

Partial Response:

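### Local tolerability has one on-treatment rating, at Week 2, with no stated recall window, so the primary safety proportions can understate reactions over the two weeks

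*Combined protocol and SAP*

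**What the plan says.** Section 3.4 makes investigator and participant ratings of four local symptoms (itching, swelling, stinging/burning, dryness) the primary safety endpoint, each on a four-point scale from none (0) to severe (3), and has "Safety endpoints to be measured at the initial and final visits". The form in the attachments (Section 15), the "Primary Safety Endpoints Table", has columns for Weeks 0 and 2 only. It has no field for worst severity and no recall instruction. The visit lists and schedule (Sections 6.1, 6.5, 6.6) add no instruction on this rating and plan no contact between visits. The advertisement agrees: "The study includes 2 visits over 2weeks".

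The Week 0 rating is untreated. The formulation is dispensed at that visit, and under Section 5.2 "An investigator will demonstrate correct application by using a bland emollient moisturizer".

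For the analysis, the safety paragraph of Section 7.2.1 states that "the proportion of patients in each category at each follow-up time point will be estimated" for each safety endpoint. Only one follow-up point exists, Week 2.

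Adverse events are handled separately. Section 6.6 has physician and participant adverse event rows at Visit 2. Section 8.2 requires specific questioning at each contact and the recording of every event in the study period.

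**The concern.** The primary hypothesis in Section 7.2.1 concerns effectiveness and tolerability together, so these proportions carry half of the study's claim. Irritation from a topical product can come and go within two weeks. The protocol itself foresees this kind of course: Section 5.2 lists discomfort from the product among the causes of poor compliance, and the stopping rule in Section 8.5 turns on whether dermatitis resolves when the cream is applied less often. A participant who reacted, used less cream and had settled by the final visit could show a clean Week 2 rating. The published proportions would then describe how skin looked and felt on one day near the end, while a reader would take them as the experience of two weeks of treatment. A larger study planned on that figure would start from too favourable a picture.

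**Working it through.** The plan states no event rate, duration, onset pattern or power for tolerability (Section 7.1 waives the calculation), so there is no figure to reproduce.

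**What the documents fix.** Ratings are at Weeks 0 and 2 (Section 3.4 and the form). The final visit is at day 14, window 13 to 15 (Section 6.5). Application is twice daily over the two-week visit schedule (Section 5.2). There are ten participants (Section 7.1). One on-treatment rating therefore stands for 2 × 14 = 28 applications, or 2 × 13 = 26 to 2 × 15 = 30 across the visit window.

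**What is undefined.** Neither Section 3.4 nor the form says whether the Week 2 score means status at the visit or worst severity since Week 0. Skindex-16, in contrast, asks about the past week. The wording of Sections 3.4 and 7.2.1 points to status at the visit, and the arithmetic below takes that reading.

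**Share of reactions still present at the visit.** Assumptions, none from the documents: one episode lasting *d* days, onset uniform over the *T* days to the visit, no recurrence. Then the share caught is *d*/*T*.

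| Duration | T = 13 | T = 14 | T = 15 |
|---|---|---|---|
| 1 day | 1/13 = 8% | 1/14 = 7% | 1/15 = 7% |
| 3 days | 3/13 = 23% | 3/14 = 21% | 3/15 = 20% |
| 7 days | 7/13 = 54% | 7/14 = 50% | 7/15 = 47% |

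Earlier onset lowers these shares; persistence or recurrence raises them.

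**Effect with ten participants.** Let *p* be an assumed two-week incidence of a reaction. The chance that no participant still has one at day 14 is (1 − *p·d*/14)^10. For *p* = 0.30:

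- *d* = 1: (1 − 0.0214)^10 = 0.81
- *d* = 3: (1 − 0.0643)^10 = 0.51
- *d* = 7: (1 − 0.15)^10 = 0.20

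A worst-grade rating with perfect recall would show at least one case with probability 1 − 0.70^10 = 0.97. Over *p* from 0.20 to 0.50 and *d* from 1 to 7 days, the chance of seeing none at day 14 runs from (1 − 0.25)^10 = 0.06 to (1 − 0.0143)^10 = 0.87.

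**What 0 of 10 would mean.** The exact one-sided 95% upper limit is 1 − 0.05^(1/10) = 25.9%; the upper end of the two-sided interval is 1 − 0.025^(1/10) = 30.8%. Under the status reading, either limit bounds prevalence at the visit and not incidence over two weeks.

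**Check on the remedy.** A worst grade over 14 days cannot fairly be compared with a single Week 0 rating. If an inert cream were used and itch independently exceeded its Week 0 grade on 5% or 10% of days (assumed), the two-week worst would exceed Week 0 in 1 − 0.95^14 = 51% or 1 − 0.90^14 = 77% of participants. The baseline needs the same window.

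**The case against.** The strongest reply is that the study does look for these reactions. Section 8.2 asks for specific questioning and complete recording. Section 8.1 counts worsening of a pre-existing condition as an adverse event. Section 8.3.1 records date, severity, relationship and resolution. A reader might infer that settled reactions go unrecorded; the documents do not support that. What remains is that this record does not feed the 0-3 proportions. Its severity scale is unspecified, so it need not map onto the four grades, and the questioning is not tied to the four symptoms. It also depends on the same two-week recall as a worst-grade item, so recall is no reason to prefer the present form. Skindex-16 does not fill the gap: it covers only the last week and has no item on swelling or dryness.

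A reader might also infer that every settled reaction is scored none. That goes too far. The recall window is undefined, so a rater might score the whole period. Itching and swelling are also disease symptoms, so a settled flare may return to a level above zero. A participant who withdraws because of a reaction has no Week 2 rating (Section 4.4.1), which is missing data and a separate gap.

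Nor can one say that first-week reactions lasting up to 7 days are never caught: at a day-13 visit, a 7-day reaction that began after day 6 is still present.

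Finally, visit-based ratings are defensible in a ten-patient open-label pilot with descriptive safety proportions. That limits the weight of the point, but the remedy is cheap and the pilot is meant to inform a larger study.

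**Conclusion.** The point holds in a limited form. One on-treatment rating, without a stated recall window and analysed at a single follow-up point, can understate local reactions over the two weeks. That the proportions rest on this one rating follows directly from Sections 3.4, 6.5 and 7.2.1 and the form. That settled reactions drop out of them depends on raters scoring status at the visit, which is the natural reading but is not stated. The undefined window is itself a weakness, since raters could differ.

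The size is illustrative only: about 7%, 21% and 50% of reactions lasting 1, 3 and 7 days caught at day 14, for single episodes with uniform onset. The documents give neither onset nor duration. The consequence is a tolerability summary that may be too favourable, not a loss of safety events from the study. It should be corrected before the form is used.

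**What to change.** In the Primary Safety Endpoints Table, for each of the four symptoms:

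- At Visit 2, keep the current rating, label it as status at the visit, and add *worst grade since first application* (0-3). The participant gives this rating; the investigator's grade is informed by the adverse event questioning, because no contact is scheduled between visits.
- At Week 0, add *worst grade in the past 2 weeks* (0-3), so that the baseline and on-treatment windows match.

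In Section 7.2.1, report the distribution of the worst on-treatment grade as a tolerability summary together with the Week 2 status, and compare the worst grade only with the matched-window baseline.

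The cost is a few extra items on an existing form, with no extra visit or contact. The drawbacks are two-week recall, and a tolerability figure that may look less favourable than the Week 2 status alone.

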4.1 Inclusion criteria

Informed subject consent will be obtained from those patients with the following inclusion criteria:

- Biopsy proven cutaneous mastocytosis with or without evidence of systemic disease
- Male and female patients 18 to 80 years of age
- No UVB treatment of the skin for 6 months prior to study entry
- No use of topical or systemic corticosteroids for 1 month prior to study entry
- Good general health as confirmed by medical history
- Female patients of child-bearing potential with negative urine pregnancy test who agree to use effective methods of birth control or remain abstinent during treatment. Participants must use birth control for the entire study and for at least 1 week after the last application of the study formulation. Acceptable methods of birth control include ongoing hormonal contraception methods, (such as birth control pills, patches, injections, vaginal ring, or implants), barrier methods (such as a condom (for men) or diaphragm used with a spermicide), intrauterine devices, tubal ligation, or abstinence.
- Patients who are willing and capable of cooperating to the extent and degree required by the protocol; and
- Patients who read and sign an approved informed consent for this study

4.2 Exclusion criteria

Patients are to be excluded based on the following criteria:

- Vulnerable study population
- •Exposure to ultraviolet B (UVB) radiation to any region of the skin surface for 6 months
- •Regular use of skin lightening agents within 1 month of study entry, including
 - °Topical corticosteroids
 - Topical bleaching products
 - Topical retinoids
- •Use of systemic preparations within 1 month of study entry, including:
 - °Systemic corticosteroids
 - °Systemic cyclosporine, interferon
 - °Systemic acitretin, etretinate, isoretinoin
 - •Systemic methotrexate,
 - °Systemic photoallergic, phototoxic and/or photosensitizing drugs
- •UV light therapy and sunbathing

- •Inability to communicate or cooperate with the Principal Investigator and/or Investigators due to language problems, poor mental development or impaired cerebral function
- •Pregnant or nursing women
- Women planning a pregnancy within the study period

4.3 Subject Recruitment, Enrollment and Screening

Subjects will be recruited from the Division of Allergic Diseases at the Mayo Clinic in Minnesota outpatient clinical practice. Patients will be provided with a Research Participant Consent and Privacy Authorization Form describing the study formulation, protocol, inclusion and exclusion criteria, as well as risks and benefits of participation.

4.4 Early Withdrawal of Subjects

4.4.1 When and How to Withdraw Subjects

Patients are free to withdraw at any time and for whatever reason. No data will be collected for withdrawn subjects and withdrawn subjects will not be replaced. There will be no follow-up for withdrawn subjects. Pre-specified reasons for discontinuing include, but are not limited to, the following:

- Patient request: Patient decided that he/she did not want to continue (for any reason).
- •Adverse Event: Patient experienced a related or unrelated event that would interfere with the study objectives/evaluation
- •Lost to Follow-up: Patient did not come in for a visit and could not be reached by phone
- Treatment Failure: If in the Principal Investigator's judgment, the patient's condition required another form of treatment
- •Noncompliance: Patient is not complying with the protocol requirements (i.e. visit schedule, dosing, regimen, etc.); a patient is to be withdrawn if he/she misses two consecutive visits
- •Other: Any other reason

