4.4.2 Data Collection and Follow-up for Withdrawn Subjects

If a Participant withdraws from the study, no additional attempts will be made to contact the Participant.

5 Study Drug

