7.3 Subject Populations(s) for Analysis

Each participant who received the study drug will be included in the primary analysis regardless of study withdrawal for any reason. In the event of any study withdrawals, in secondary analysis we will examine the sensitivity of our results to the exclusion of patients who withdrew.

8 Safety and Adverse Events

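### Sections 7.3 and 7.2.1/4.4 conflict on how a treated patient without a Week 2 outcome counts in the primary response proportion

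*Combined protocol and SAP*

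**What the plan says.** The primary endpoint (3.2, and Primary Hypothesis under 7.2.1) is the proportion of participants with a complete or near-complete response after two weeks. Section 7.1 sets the sample at 10 without a calculation.

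- **Who is analysed (7.3).** "Each participant who received the study drug will be included in the primary analysis regardless of study withdrawal for any reason". If anyone withdraws, a secondary analysis follows: "we will examine the sensitivity of our results to the exclusion of patients who withdrew".
- **What is collected after withdrawal (4.4.1, 4.4.2).** "No data will be collected for withdrawn subjects and withdrawn subjects will not be replaced". Also: "If a Participant withdraws from the study, no additional attempts will be made to contact the Participant".
- **When response is measured (6.5, 6.6).** Visit 2, at Week 2 with a one-day window either side, is the only assessment after baseline.
- **What happens to missing data (7.2.1).** None is expected. If some occurs, "no attempt to impute this missing data will be made", and "missing data will simply be treated as missing in the statistical analysis".
- **How response is classified (7.2.1).** All four categories, including no response, are defined by change in SCORMA, SkinDex-16 or lesions. None covers a patient who was not assessed.

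**The concern.** A treated patient who leaves before Visit 2 is in the primary analysis under 7.3 but has nothing from which a response category could be assigned. The plan does not say whether that patient stays in the denominator of the proportion.

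If the missing-data sentence is applied to the proportion, the patient drops out of it. The primary analysis then no longer covers everyone treated, contrary to 7.3. The secondary analysis also loses its purpose for these patients, because they are absent from both sides of the comparison.

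The listed reasons for withdrawal include treatment failure and adverse events. Removing such patients would tend to raise the reported response rate. Section 7.1 says the estimate is meant to help design a larger study, so the denominator should be fixed before open-label results are seen. The Week 2 tolerability ratings of 3.4 are missing for the same patients.

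**Working it through.** The plan gives no response rate, dropout rate or power figure to reproduce, so the check is of the rules and then of an illustration.

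**Step 1: the rules side by side.** Take a patient who receives drug and leaves before Visit 2.

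1. Section 7.3: the patient is in the primary analysis.
2. Sections 4.4.1 and 4.4.2: no data are collected and no contact is attempted.
3. Sections 6.5 and 6.6: there is no earlier post-baseline score to use.
4. Section 7.2.1: nothing may be imputed, and no category fits.

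Rules 1 and 4 cannot both be applied to a proportion without a further statement. A patient withdrawn at Visit 2 itself is different. Section 5.2 weighs the jars at that visit, so a withdrawal for noncompliance could come with Week 2 scores already recorded. For that patient the 7.3 comparison does work.

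**Step 2: size.** Assume all 10 patients are treated, *r* respond, and *w* have no Week 2 outcome.

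- All treated: r/10
- Completers only: r/(10 − w)
- Best case, every unassessed patient counted as a responder: (r + w)/10
- Completers only minus all treated: r·w / [10(10 − w)]

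With r = 5 (exact Clopper-Pearson 95% intervals in brackets):

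| w | All treated | Completers only | Best case |
|---|---|---|---|
| 0 | 5/10 = 50.0% (18.7–81.3) | 50.0% | 50.0% |
| 1 | 50.0% | 5/9 = 55.6% (21.2–86.3) | 6/10 = 60.0% (26.2–87.8) |
| 2 | 50.0% | 5/8 = 62.5% (24.5–91.5) | 7/10 = 70.0% (34.8–93.3) |
| 3 | 50.0% | 5/7 = 71.4% (29.0–96.3) | 8/10 = 80.0% (44.4–97.5) |

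Completers-only exceeds all-treated by 5.6, 12.5 and 21.4 points for w = 1, 2 and 3.

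With w = 1 the difference is r/90: 1.1 points for r = 1, 5.6 for r = 5, and 10.0 for r = 9.

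**Step 3: direction.** If every unassessed patient would have responded, the true figure is the best case. Completers-only is then too low, by 60.0 − 55.6 = 4.4, 70.0 − 62.5 = 7.5 and 80.0 − 71.4 = 8.6 points. Upward bias is therefore likely from the listed reasons but is not guaranteed.

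**Step 4: how often it could arise.** With an assumed independent chance *d* per patient of having no Week 2 outcome, the chance of at least one in ten is 1 − (1 − d)^10. This is 0.40, 0.65 and 0.89 for d = 5%, 10% and 20%.

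**The case against.** The strongest reply is that 7.3 already settles the matter. It keeps withdrawn patients in the primary analysis, and a sensitivity analysis that removes them makes sense only if they counted there. The Primary Hypothesis speaks of participants who achieve a response, which an unassessed patient has not been shown to do. On that reading the plan intends r/10, with completers-only as the sensitivity analysis. This largely stands: r/10 is the better reading, and the two readings are not equally supported. What remains is that the missing-data sentence, applied as written, gives the other answer, and no sentence says which prevails.

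A second reply is that the consequence is small. The study is an uncontrolled pilot of 10 patients over two weeks. The response proportion has no threshold, comparator or go/no-go rule. One unassessed patient with 5 responders moves the estimate by 5.6 points, against an exact interval for 5/10 about 63 points wide. That also stands, and it limits the severity.

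Two stronger readings are tempting but not supported.

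- A reader might infer that the plan has no missing-data rule. It has one; the trouble is that it collides with 7.3.
- A reader might infer from 4.4.1 that a patient who misses Visit 2 but can be reached cannot be withdrawn, because that section mentions "Patient did not come in for a visit and could not be reached by phone" and "a patient is to be withdrawn if he/she misses two consecutive visits". Neither is a precondition for withdrawal. The list is expressly open-ended and includes patient request, noncompliance with the visit schedule, and any other reason. Such a patient may or may not be withdrawn. Either way, no response category follows.

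**Conclusion.** The conflict is in the current text and should be resolved, but it is minor: a reconciliation of analysis rules in an exploratory pilot. Section 7.3 points to all treated patients as the denominator. Section 7.2.1, taken with 4.4, leads to completers only.

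For 5 responders and 1 to 3 patients without Week 2 data, the choice moves the primary estimate by 5.6 to 21.4 points. These counts are assumed, since the documents give no response or dropout rate and 7.2.1 expects no missing data. If every treated patient has a Week 2 outcome, there is no effect.

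A reader might infer that the reported response rate will be inflated. The documents do not support that. Inflation requires patients without Week 2 data, the completers-only reading, and unassessed patients who would have done worse than those assessed. Patient request, unrelated events and loss to follow-up are also listed reasons for withdrawal, and they need not point that way.

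**What to change.** **In 7.2.1 and 7.3.** State that:

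- the denominator of the primary proportion is all treated patients;
- a patient without a Week 2 outcome, withdrawn or not, counts as a non-responder;
- treating data as missing does not remove a patient from this denominator.

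Report the completers-only and best-case proportions as sensitivity analyses, with exact 95% intervals. The no-imputation rule can stand for the continuous changes in SCORMA and SkinDex-16.

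**In 4.4.** State that data already collected are kept; 9.1 says this only for revoked authorization. Reconcile the no-data, no-follow-up and no-contact wording with the adverse-event recording and follow-up in 8.1 and 8.2. Offering the existing Visit 2 assessments at withdrawal, to a patient who agrees, is optional.

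**Cost.** Wording only, unless the optional assessment is adopted. If the sponsor already intends r/10, the reported rate does not change. If it intends completers-only, the rate falls when Week 2 data are missing, for example by 5.6 points with 5 responders and one such patient. Non-responder counting can understate the rate by up to 1/10 = 10 points for each unassessed patient who would have responded; the best-case analysis shows that limit.
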